5.6 General Considerations

Unless otherwise stated, all hypotheses will be tested at 0.95% confidence interval (p = 0.05, two-sided test, when applicable). In other words, statistical test will look for the difference (either better results or worse results), rather than focusing solely on efficacy. All continuous measurements will be summarised descriptively at each visit, followed by treatment, using observed data.

Summary of continuous variables will be presented using the total number of participants (N), Mean, Standard Error of mean (SE), Standard Deviation (SD), Median and Range (Minimum and Maximum). The categorical variables will be presented using the number and the percentage of subjects who have provided the defined categorical answer.

For measurements obtained during course of time, mean values will be plotted to explore the trends. Observed data will be used as the basis for plotting data along with standard error (SE) or Standard Deviation (SD) represented as bars, if not otherwise specified.

A non-parametric Mann-Whitney U Test (or Wilcoxon Rank-Sum Test) will be applied on primary and secondary efficacy endpoints to test the significance of the effects of the treatment by comparing median values.

For measurements performed over time, median values will be plotted to explore the trends. Observed data will be used as the basis for plotting the data along with Inter Quartile Range (IQR) used as bars, if not otherwise specified.

A parametric, repeated measurements ANOVA will be applied as a sensitive analysis to test the significance of the effects of the treatment.

Change from baseline safety Lab measurements will be analyzed using a repeated measurements ANOVA to test the significance of the effects of the treatment.

Presentation of results from a statistical analysis model will include the estimated means caused by treatment effects, using Adjusted Mean. HB-adMSCs 200MM vs Placebo group will be compared.

For all endpoints analyzed statistically, estimated mean treatment differences will be presented together with two-sided 95% confidence intervals and p-values.

All safety evaluations will be presented using Safety analysis set while the efficacy analysis

Individual safety and efficacy parameters will be listed.

will be presented using Efficacy analysis set.

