7. EFFICACY ANALYSES

7.1. Primary Efficacy Analyses

7.1.1. Endpoint / Variables

The primary efficacy endpoint is difference between the Baseline value in Total MDS-UPDRS Part II score and the value measured at the end of the study (Week 52).

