7.1.2. Summary Measure

Least Square Means using parametric RMA model. Median values using Non-parametric method.

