7.1.4.1. Statistical Methodology Specification

Primary endpoint will be analyzed using the Mann-Whitney U Test (or Wilcoxon Rank-Sum Test) for the comparison of HB-adMSCs 200MM vs. Placebo.

Sensitivity analysis

Sensitivity analysis will be performed on Efficacy analysis set using a repeated measurements ANOVA model to evaluate the robustness of using parametric method. If the normality of dataset shows significant violation from the presumption of normality, the parametric method will not be performed.

All primary endpoint efficacy measurements available at post-baseline at scheduled measurements will be analyzed using Repeated Measures ANOVA. The model will include treatment, visits as fixed factors. The within subject factor is visit and with 7 levels (Weeks 4, 8, 16, 24, 32, 42 and 52). The between-subjects factor is treatment (HB-adMSCs 200MM or Placebo).

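### The primary Mann-Whitney test has no matching effect estimate or confidence interval, and the mean difference that the SAP promises in its place comes from a model that does not target Week 52 and may not be run

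*SAP*

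**What the plan says.** **Test.** SAP 7.1.4.1: "Primary endpoint will be analyzed using the Mann-Whitney U Test (or Wilcoxon Rank-Sum Test) for the comparison of HB-adMSCs 200MM vs. Placebo". SAP 7.1.1 and 2.3 place the primary endpoint at Week 52 only. SAP 5.6 says that the rank test is applied "to test the significance of the effects of the treatment by comparing median values".

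**Summary measure.** SAP 7.1.2: "Least Square Means using parametric RMA model. Median values using Non-parametric method". SAP 7.2.2 does the same for the secondary endpoints.

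**Estimate and interval.** SAP 5.6: "For all endpoints analyzed statistically, estimated mean treatment differences will be presented together with two-sided 95% confidence intervals and p-values". The same section adds: "Presentation of results from a statistical analysis model will include the estimated means caused by treatment effects, using Adjusted Mean".

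**The model.** The repeated measures ANOVA in SAP 7.1.4.1 is a sensitivity analysis over Weeks 4, 8, 16, 24, 32, 42 and 52. Its terms are given as: "The model will include treatment, visits as fixed factors". No treatment-by-visit term and no Week 52 contrast is named.

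**The condition.** SAP 7.1.4.1: "If the normality of dataset shows significant violation from the presumption of normality, the parametric method will not be performed".

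No Hodges-Lehmann estimate, probability-of-superiority measure, interval for a difference in medians, or location-shift assumption appears in the text.

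**The concern.** A rank-sum test asks whether values in one arm tend to exceed those in the other. It becomes a test of medians, or of means, only if the two distributions differ by a pure shift, and the SAP does not assume that. So neither the arm medians nor a mean difference is the estimate that goes with the primary p-value.

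The promised interval has a second problem. Its only specified source among the efficacy analyses is a model that targets another quantity, and that model is dropped when normality fails. Section 5.6 then requires an interval for which 7.1.4.1 leaves no specified method.

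The protocol randomises 12 patients per arm, SAP 10.1.2.1 excludes patients with missing data, and neither document states an effect size, SD or power. In a trial of this size the interval is the main evidence on which effects can be ruled out, so it should be defined and should belong to the primary test.

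**Working it through.** **Plan figures.** There is no planned effect or SD to reproduce. The 95% interval does match the 5% two-sided level in SAP 2.3 (1 − 0.95 = 0.05).

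**1. What the ANOVA treatment effect estimates.** With complete data and only treatment and visit terms, it is the equally weighted average of the seven visit differences. Suppose the true effect grows linearly to D at Week 52:

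- Sum of visit weeks: 4 + 8 + 16 + 24 + 32 + 42 + 52 = 178.
- Average effect: (178 / 7) / 52 × D = 25.43 / 52 × D = 0.49 D.

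The model would report about half of the Week 52 effect. If the effect is D at Weeks 42 and 52 and zero before, it reports 2/7 = 0.29 D. These time courses are illustrations, not predictions.

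**2. What is left when normality fails.** Section 5.6 asks for a mean difference and interval for every endpoint analysed statistically. Section 7.1.4.1 cancels the model that gives them. What remains specified is the rank p-value, the arm medians, and descriptive means, SDs and SEs by visit.

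**3. How often the two methods disagree.** Assumptions: integer change scores, SD 4, true shift 3 points, 12 per arm, 8,000 simulated trials. The Mann-Whitney p-value is compared with a two-sample t 95% interval for the Week 52 mean difference. The SAP names no normality test, so Shapiro-Wilk on residuals at 5% is assumed. The t interval stands in for a Week 52 interval; it is not the SAP's ANOVA.

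| | Normal errors | Strongly skewed errors (gamma, shape 1) |
|---|---|---|
| Normality check removes the model | about 5% | about 80% |
| Rank p<0.05 but mean interval includes 0, ignoring the check | – | about 15% of all trials |
| The same, with the model still run | 1.4% of all trials | about 0.2% of all trials |

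With normal errors, disagreement in either direction is about 7% of all trials. A separate set of 10,000 trials per scenario (SD 5, normal errors) gives 1.8% under no effect, 7.2% at a 0.8 SD shift and 6.1% at a 1.14 SD shift.

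**4. A constructed example (12 v 12).**

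- Active: −6, −5, −5, −4, −4, −3, −3, −2, −2, −1, 15, 20 (mean 0).
- Placebo: −1, 0, 0, 0, 1, 1, 1, 2, 2, 3, 3, 4 (mean 16/12 = 1.33).

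The rank p is 0.0065. The mean difference is −1.33 (95% interval −6.42 to 3.76). The Hodges-Lehmann shift is −4.0 with rank-based interval −6 to −2 (critical U = 37, exact two-sided level 4.49%), which agrees with the test. The assumed check would reject normality here (p = 0.00001), so under 7.1.4.1 the conflicting model would be dropped and no specified interval would replace it.

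**5. Ties.** Take active −9, −8, −7, −6, −5 and seven zeros, against placebo seven zeros and 3, 4, 5, 6, 7. The rank p is 0.0024, yet both arm medians are 0. The Hodges-Lehmann shift is −5 with interval −8 to 0. Equal medians with a significant rank test are possible, but occurred in none of the simulated trials. The example also shows that a rank-based limit can touch 0 under heavy ties.

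**The case against.** **The interval could come from elsewhere.** The sentence in 5.6 is not tied to the ANOVA, and the descriptive means and SDs would allow a mean difference and interval to be calculated. The planned displays that the SAP refers to are also not visible. This stands in part: it would be too strong to infer that the primary can have no interval at all. What the text supports is that 5.6 and 7.1.4.1 conflict and that no interval method is specified when the model is dropped.

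**Contradictory results would be rare.** A reader might infer from the 15% in skewed data that the published interval would often contradict the p-value. The SAP's own condition removes most of those intervals and leaves about 0.2%. Contradiction and a missing interval are alternatives and cannot be added together. With normal errors, 15% of the trials significant by either method show disagreement, but over all trials it is about 7%. This objection stands.

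**The simulation uses a pure shift.** Under a shift, the mean difference, median difference and Hodges-Lehmann shift have the same true value, so the disagreement reflects the different efficiency of two methods. That is correct. The mismatch of target rests on the absence of any shift assumption in the SAP and on the averaging over visits, not on the simulation.

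**Medians are already paired with the rank test.** SAP 7.1.2 does this, and nothing calls the mean difference the headline result. True, but two arm medians are neither a treatment-effect estimate nor an interval.

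**Conclusion.** The point holds in this form: the primary rank test has no matching estimate or interval, its description as a comparison of medians is wrong without a shift assumption, and the promised mean difference rests on a sensitivity model that averages over visits and is conditional on normality.

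The documents do not support reading this as a flaw in the primary test. Its p-value and error rate do not change. Nor do they support a claim of frequent contradiction. With near-normal data, disagreement is about 2% to 7% of all trials. With strongly skewed data, the usual result is no specified interval (about 80% of trials under the assumed check).

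All of these percentages depend on the assumed SD, shift, error shape and normality test, since the documents give none of them. The conflict between 5.6 and 7.1.4.1, and the lack of a Week 52 contrast in the model, depend on none of these. The change is worth making because it decides which primary estimate and interval are reported.

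**What to change.** In SAP 5.6, 7.1.2 and 7.2.2:

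- For each Mann-Whitney comparison, report the Hodges-Lehmann shift at that visit, with the 95% confidence interval from inverting the same test.
- State how ties are handled in the test and the interval, and what will be reported if a limit falls on 0 while p<0.05.
- Delete the statement in 5.6 that the test compares medians. Keep arm medians as description.
- Confine model-based mean differences to the parametric sensitivity analysis, and amend the promise in 5.6 so that it no longer conflicts with 7.1.4.1.

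The cost is a few lines of SAP wording. The estimate and interval are standard software output and need no new data.

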6. STUDY POPULATION ANALYSES

6.1. Overview of Planned Study Population Analyses

The study population analyses will be based on the Safety analysis set.

Study population analyses includes analyses of subject disposition, demographic, as well as characteristics compared to baseline, including medical history, prior and concomitant medications.

Details of the planned displays are presented in Error! Reference source not found..

Categorical variables will be summarized by the number and percentage of subjects who provided a specific answer, and the continuous parameters will be summarized by N, mean, standard error of mean, median, sample standard deviation, minimum and maximum, unless otherwise specified.

Disposition summary includes subject screened and randomized, while the disposition at end of study, Week 52, along with reasons for withdrawals will be presented based on number of subjects and percentage. Subjects in different analysis sets also will be presented.

The reasons for screening failure will be presented based on number of subjects and percentage. The percentage will be calculated based on the total number of screened subjects.

7. EFFICACY ANALYSES

7.1. Primary Efficacy Analyses

7.1.1. Endpoint / Variables

The primary efficacy endpoint is difference between the Baseline value in Total MDS-UPDRS Part II score and the value measured at the end of the study (Week 52).

7.1.2. Summary Measure

Least Square Means using parametric RMA model. Median values using Non-parametric method.

7.1.3. Population of Interest

The primary efficacy analyses will be based on the Efficacy analysis set population, unless otherwise specified.

7.1.4. Statistical Analyses / Methods

Details of the planned displays are provided in Error! Reference source not found..

7.1.4.1. Statistical Methodology Specification

Primary endpoint will be analyzed using the Mann-Whitney U Test (or Wilcoxon Rank-Sum Test) for the comparison of HB-adMSCs 200MM vs. Placebo.

Sensitivity analysis

Sensitivity analysis will be performed on Efficacy analysis set using a repeated measurements ANOVA model to evaluate the robustness of using parametric method. If the normality of dataset shows significant violation from the presumption of normality, the parametric method will not be performed.

All primary endpoint efficacy measurements available at post-baseline at scheduled measurements will be analyzed using Repeated Measures ANOVA. The model will include treatment, visits as fixed factors. The within subject factor is visit and with 7 levels (Weeks 4, 8, 16, 24, 32, 42 and 52). The between-subjects factor is treatment (HB-adMSCs 200MM or Placebo).

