A repeat measure mixed model will be used to assess within-subject changes from baseline. correction for multiple comparisons will be employed for post-hoc comparisons. Parkinson's assessment scores (i.e., MDS-UPDRS) at screening and infusion 1 (before treatment) will be averaged and treated as a baseline. Averaging is performed to minimize sources of variance (i.e., patient condition, assessors) and particularly to establish a reliable baseline from which to establish changes.

Data Handling Case Report Forms (CRF)

As used in this protocol, the term CRF should be understood to refer to either a paper form or an electronic data record or both. Reports received by the site, or from the central laboratory should be printed, retained as source documentation and signed by the principal investigator, indicating which values are considered clinically significant and to be reported as AEs if applicable.

Source data is all information, original records of clinical findings, observations, or other activities in a clinical trial necessary for the reconstruction and evaluation of the trial. Source data are contained in source documents

Changes in the Conduct of the Clinical Trial Protocol Amendments

Any change to the protocol will need to have a protocol amendment submitted to the IND, and FDA and IRB must agree prior to proceeding.

Deviations from the Protocol

Deviations from the protocol should not occur. If safety deviations occur, the principal investigator must inform the Monitor, and the implications of the deviations must be reviewed and discussed. Any deviation must be documented in the protocol deviation log. In addition, each deviation must include a description of the deviation, the relevant dates (start and stop), and the action taken. All deviation reports and supporting documents must be kept in the Investigator Site File and in the Trial Master File.

Premature Clinical Trial Termination

Both the Study Investigator and Sponsor have the right to terminate the clinical trial at any time. Should this become necessary, the procedures will be agreed upon after consultation between the two parties. In terminating the clinical trial, the Sponsor and the Study Investigator will ensure that adequate consideration is given to the protection of the best interests of the study participants. Regulatory authorities and IRB will be informed.

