• To investigate the safety and efficacy of intravenous infusions of HB-adMSCs vs Placebo in patients with Parkinson's disease as determined by improvements in Quality of Life, estimated by the MDS UPDRS assessment. (Time frame: Baseline to Weeks 4, 8, 16, 24, 32, 42 and 52). A battery of statistical tests will be applied, where suitable and applicable. Tests will include the report of parametric or non-parametric statistical tests, with the corresponding p-values, presented in pair-wise manner, as well as contingency tables, representing answers in their native form.	 Change from Baseline in Total MDS-UPDRS Part II, only at Week 52 Number of treatment-emergent Adverse Event (TEAEs) during 52 week period Number of serious Adverse Events (SAEs) during the period of 52 weeks Number of AEs of special interest includes thromboembolic events, peripheral events defined as thromboembolism of the extremities, infections and hypersensitivities Change from baseline in clinical parameters, measured at the end of the study (52 weeks): Physical examination Electrocardiogram (ECG) Pulse Systolic blood pressure Body weight BMI Change from baseline in laboratory assessments at the end of the study (52 weeks):

Protocol Number: HBPD03

Date: 18-Apr-2023 Version: 2.0 Hope Biosciences Statistical Analysis Plan Status: Final

Objectives	Endpoints
	o Biochemistry
	 Haematology
	 Urinalysis
Secondary Objectives	Secondary Endpoints
To evaluate the safety and efficacy of intravenous infusions of HB-adMSCs vs Placebo in patients with Parkinson's disease based on	Change from Baseline in MDS- UPDRS Total score, at all the timepoints collected, during the period of study (52 Weeks)
changes in disease assessments and dosage of medications. (Time frame: Baseline to Weeks 4, 8, 16, 24, 32, 42 and 52).	 Change from Baseline in Total MDS- UPDRS Part I, at all the timepoints collected during the period of study (52 Weeks)
	 Change from Baseline in Total MDS- UPDRS Part II, at all the timepoints collected during the period of study (52 Weeks)
	 Change from Baseline in Total MDS- UPDRS Part III at all the timepoints collected during the period of study (52 Weeks)
	 Change from Baseline in Total MDS- UPDRS Part IV, at all the timepoints collected during the period of study (52 Weeks)
	 Change from Baseline in Total Neuro- Quality of Life Assessments scores (Neuro-QOL), at all the timepoints collected during the period of study (52 Weeks)

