5.3 Examination of Covariates, Other Strata and Subgroups

5.3.1 Covariates and Other Strata

Baseline will be included as a covariate in the efficacy analyses, wherever applicable.

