7.2.4.1. Statistical Methodology Specification

Secondary endpoints will be analysed using the Mann-Whitney U Test (or Wilcoxon Rank-Sum Test), for the comparison of HB-adMSCs 200MM vs. Placebo.

Sensitivity analysis

Sensitivity analysis will be performed on Efficacy analysis set using a repeated measurements ANOVA model to evaluate the robustness of using parametric method. If the normality of dataset shows significant violation from the presumption of normality, the parametric method will not be performed.

All secondary endpoint efficacy measurements available at post-baseline at scheduled measurements will be analyzed using Repeated Measures ANOVA. The model will include treatment, visits as fixed factors. The within subject factor is visit and with 7 levels (Weeks 4, 8, 16, 24, 32, 42 and 52). The between-subjects factor is treatment (HB-adMSCs 200MM or Placebo).

For Levadopa, the comments will be made about the total number of patients have reduced the dose of medication.

Proportion of subjects requiring reinstatement of PD medication dose

Patients are defined as having reinstated with PD medication if, at any time during the study, their medication dose reinstated up to, or above, their baseline level after it has Page 12 of 15

been reduced. Number of subjects who have reinstated PD dose will be summarized using count and percentage.

Reinstatement is not applicable for patients who did not reduce their dose during the study.

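### The repeated-measures model behind the primary endpoint's mean difference and 95% CI estimates an average over Weeks 4 to 52, not the Week 52 difference, and does not list baseline

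*SAP*

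**What the plan says.** The SAP's table of objectives and endpoints defines the primary efficacy endpoint as "Change from Baseline in Total MDS-UPDRS Part II, only at Week 52", and SAP 7.1.1 agrees. The hypothesis is tested with a Mann-Whitney test (SAP 7.1.4.1).

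Two sections ask for a model-based estimate as well. SAP 7.1.2 gives the summary measure as "Least Square Means using parametric RMA model", alongside medians from the non-parametric method. SAP 5.6 states that, for every endpoint analysed statistically, "estimated mean treatment differences will be presented together with two-sided 95% confidence intervals and p-values".

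The only parametric model specified for this endpoint is the repeated-measures ANOVA in SAP 7.1.4.1, labelled a sensitivity analysis: "The model will include treatment, visits as fixed factors". Visit has seven levels (Weeks 4, 8, 16, 24, 32, 42 and 52), and treatment is the between-subjects factor. SAP 7.2.4.1 uses the same specification for the secondary endpoints.

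SAP 5.3.1 says "Baseline will be included as a covariate in the efficacy analyses, wherever applicable". Baseline does not appear among the terms in 7.1.4.1 or 7.2.4.1.

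**The concern.** With treatment and visit as the only terms, the model assumes one treatment difference common to all visits. The least-squares means and CI it supplies would sit beside a Week 52 test but answer a different question. A benefit that builds over time would be understated. A benefit present during the infusions and lost by Week 52 could still be reported as a treatment difference.

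The model is also meant as a sensitivity analysis. If it targets a different quantity from the Mann-Whitney test, neither agreement nor disagreement between the two says much about the Week 52 result.

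A time-varying effect is plausible in this design: the last infusion is at Week 32 and Week 52 comes 20 weeks later.

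The baseline point is smaller. A Mann-Whitney test cannot take a covariate, so this model is the only analysis of the primary endpoint in which SAP 5.3.1 could apply, and its listed terms leave baseline out.

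**Working it through.** The documents state no effect size, SD, correlation or time course, so there is no plan figure to reproduce. Those inputs are assumed below. The visit weeks come from SAP 7.1.4.1, and 12 patients per arm from the protocol's section on randomization and blinding.

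**1. What the listed model estimates.** With complete, balanced data, the treatment coefficient in a treatment + visit repeated-measures ANOVA is the plain mean of the seven visit differences. This was checked on one simulated data set:

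| Quantity | Value |
|---|---|
| Treatment + visit coefficient | -4.822 |
| Mean of the seven visit differences | -4.822 |
| Actual Week 52 difference | -7.669 |
| Week 52 contrast with treatment-by-visit included | -7.669 |

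Week 52 therefore carries 1/7 = 14% of the weight, and the five infusion visits (Weeks 4 to 32) carry 5/7 = 71%. An assumed autoregressive covariance gives Week 52 a weight of about 0.26 to 0.41, which is still not the Week 52 difference.

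**2. Average relative to Week 52, for assumed time courses.**

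- Constant: 1.
- Linear to Week 52: (4+8+16+24+32+42+52)/(7 × 52) = 178/364 = 0.489.
- Linear to Week 32, then level: (0.125+0.25+0.5+0.75+1+1+1)/7 = 4.625/7 = 0.661.
- Peak at Week 32, linear fade to zero at Week 52: (0.125+0.25+0.5+0.75+1+0.5+0)/7 = 3.125/7 = 0.446 of the peak, while the Week 52 effect is 0.

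These ratios do not depend on the size of the effect.

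**3. Effect on the reported interval.** Assume SD 1 for the analysed change score at each visit, equal between-visit correlation r, 12 complete patients per arm and 22 degrees of freedom (critical t 2.074). Then SE of the average = √(2/12) × √((1+6r)/7).

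Example: linear growth, Week 52 effect 0.8 SD, r = 0.5. Bias = 0.8 × (1 − 0.489) = 0.409. SE = 0.408 × 0.756 = 0.309. Bias/SE = 1.32. The noncentral t distribution gives 75.5% coverage of the true Week 52 difference.

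For r from 0.5 to 0.8:

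| Assumed effect | Coverage, linear | Coverage, plateau | Rejection rate, faded to zero |
|---|---|---|---|
| 0.8 SD | 76–82% | 87–89% | 20–15% |
| 0.5 SD | 88–90% | 92–93% | 11–9% |
| 0.3 SD | 92–93% | 94% | 7–6% |

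Nominal values are 95%, 95% and 5%. In the last column the assumed effect is the Week 32 peak.

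A separate simulation fixed the raw-score SD at 6 points and the Week 52 effect at 5 points. Coverage under linear growth fell from 74% to 32% as the raw-score correlation rose from 0.5 to 0.85. The direction differs because a higher raw-score correlation shrinks the SD of the change, so the same 5 points is a larger standardised effect.

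**4. After the change.** In that simulation the Week 52 difference averaged -4.94 to -5.06 against a true -5, with 94% to 96% coverage. Adjusting for baseline left it unbiased and cut the average SE from about 2.42 to 2.14 at correlation 0.5, and from 1.88 to 1.77 at 0.7. By formula, the unadjusted variance is 2/(1+ρ) times the adjusted one, with ρ the correlation of baseline and Week 52 scores: 1.33, 1.18 and 1.11 at ρ = 0.5, 0.7 and 0.8.

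**The case against.** The strongest reply is that SAP 7.1.4.1 describes factors and is not a full list of terms. A two-way design with one between- and one within-subject factor normally carries the interaction, and some software adds it by default. The protocol also mentions corrected post-hoc comparisons, and the SAP mentions pairwise p-values. But none of these names a Week 52 contrast, and even with the interaction fitted, the treatment main effect remains a visit average. The reported quantity should not depend on a software default.

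Second, the model is a sensitivity analysis and is dropped if normality is clearly violated. The primary test is a Mann-Whitney test at Week 52, with medians also reported. This limits the consequence: the primary p-value is untouched. It does not remove the problem, because SAP 7.1.2 and 5.6 make this model the source of the means, difference and CI whenever it is run.

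Third, SAP 5.3.1 is a general rule with a qualifier, SAP 5.6 speaks of adjusted means, and 7.1.4.1 does not rule baseline out. That is fair. The two sections need reconciling more than they contradict each other, and in a randomised comparison of change scores the main cost of omission is precision.

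Fourth, the coverage figures depend on a large assumed effect. This stands in part: at 0.3 SD coverage is near nominal. The 49%, 66% and 45% ratios are unaffected.

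**Conclusion.** The concern holds. Followed as written, the model gives a Week 4 to 52 average as the mean difference for an endpoint defined at Week 52. The two coincide only if the effect is constant over visits or happens to average to its Week 52 value. Under the other assumed time courses, the model returns 49% to 66% of the Week 52 effect, or 45% of a peak that no longer exists. How far this damages the CI depends on the unknown effect size: slight at 0.3 SD, and coverage of 76–82% at 0.8 SD under linear growth. All of this assumes equal visit weights and complete data in 12 patients per arm. The missing baseline term is a lesser inconsistency that costs precision. The Mann-Whitney result stands as planned.

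**What to change.** In SAP 7.1.4.1, list treatment, visit, treatment-by-visit and baseline score. In 7.1.2, name the Week 52 treatment contrast with its 95% CI as the summary measure. Make the same correction to the model in 7.2.4.1, which is introduced by "All secondary endpoint efficacy measurements available at post-baseline at scheduled measurements will be analyzed using Repeated Measures ANOVA".

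The Protocol's Statistical Methods section already names a suitable framework: "A repeat measure mixed model will be used to assess within-subject changes from baseline". A mixed model using all available visits, with Kenward-Roger degrees of freedom, would fit that. The covariance should be specified in advance and kept small. An unstructured seven-visit matrix needs 7 × 8/2 = 28 parameters with at most 24 patients. Heterogeneous compound symmetry needs 7 + 1 = 8, with compound symmetry as a fallback. These details are advisable but secondary to the interaction and the contrast. A Week 52 ANCOVA on baseline is a simpler alternative. The Mann-Whitney test can stay primary.

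The cost is SAP wording and programming, plus a few degrees of freedom: six for treatment-by-visit, one for baseline. If the effect really is constant, precision is lost. The Week 52 CI is then 1/√((1+6r)/7) times as wide as that of the average: 1.32 at r = 0.5, 1.16 at 0.7 and 1.10 at 0.8, before any gain from baseline adjustment.
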